  - Fasting serum HDL-C  $<$  40 mg/dL (1 mmol/L) for males and  $<$  50 mg/dL (1.3 mmol/L) for females, ***or*** on pharmacological agents ***with explicit purpose*** to increase HDL-C (refer to [Section 5.8.2](#) for acceptable versus prohibited medications);

- Fasting serum triglyceride (TG)  $\geq$  150 mg/dL (1.7 mmol/L), or on pharmacological agents with explicit purpose to decrease TG (refer to [Section 5.8.2](#) for acceptable versus prohibited medications);
  - Seated blood pressure (BP)  $\geq$  130 / 85 mm Hg, or on pharmacological agents with explicit purpose for BP control (refer to [Section 5.8.4](#) for acceptable versus prohibited medications);
  - Waist circumference  $\geq$  40 inches (102 cm) for males and  $\geq$  35 inches (89 cm) for females.
11. At Visit 2 (Screen 2), liver fat of  $\geq$  8%, using MRI-PDFF acquisition protocol at the sponsor-qualified Imaging facility in close proximity to the site, confirmed via a single repeat, if deemed necessary by the sponsor-identified central imaging vendor of MRI-PDFF images – refer to [Section 7.1.4](#).
12. At Pre-Qualification, evidence of a personally signed and dated informed consent document indicating that the subject has been informed of all pertinent aspects of the pre-qualification procedures of this protocol.
- NOTE: for subjects who qualify based on Pre-Qualification procedures, at Visit 1 (Screen 1), evidence of a separate personally signed and dated informed consent document indicating that the subject has been informed of all pertinent aspects of the main study, is required;
13. Subjects willing and able to comply with scheduled visits, treatment plan, laboratory tests, and other study-related procedures as outlined herein.

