## 9.1. Sample Size Determination

The sample size for this study was based on interest to assess a dose-response for effect of PF-05221304 on percent change from baseline in liver fat (entire study population as well as separately in each sub-population in 1st tier stratification) and percent change from baseline in ALT in the 1st tier stratification sub-population of diagnosed/presumed NASH.

The proposed sample size for this study is approximately 360 subjects randomized (72 subjects per arm) to ensure at least 300 subjects (60 subjects per arm) complete the study.

The sample size of a minimum of 60 completers per arm, was calculated to yield  $\geq 80\%$  power to detect a placebo-adjusted, percent change from baseline of  $\geq 30\%$  in liver fat (in entire study population *and* in  $n=30$ /arm in each sub-population of the 1st tier stratification), using a 1-sided, t-test at level 10%. The calculation assumes that the standard deviation for liver fat is 7.8% (between-subject) and 6.2% (within-subject).

For the secondary endpoint of ALT in the 1st tier stratification sub-population of diagnosed/presumed NASH, the sample size of a minimum of 30 completers per arm was calculated to yield  $\geq 80\%$  power to detect a placebo-adjusted, percent change from baseline in ALT of  $\geq 35\%$ , using a 1-sided, t-test at level 10%. The calculation assumes that the standard deviation for the parameter of placebo-adjusted, percent change from baseline in ALT is 55% (between-subject).

Overall, via the planned interim analysis (refer to [Section 9.5](#)), if the observed standard deviation for the liver fat (MRI-PDF) and ALT data, based on unblinded review, is greater than the assumptions above, the sample size for this study *may* be adjusted upward, at sponsor discretion, to a maximum of 500 subjects randomized (ie, 100 subjects per arm).

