3.5 Baseline Variables

For each subject, for each of the following parameters, baseline will be defined as:

- Liver fat content, via MRI-PDFF, defined as the value of total mean liver fat obtained between Visit 4 and Visit 5 (ie, labeled as baseline)

CCI

- Result closest prior to dosing on Day 1 [Visit 5] for the remaining pharmacodynamic endpoints **and all** safety-related continuous endpoints
 - As such would be results as reported on Day 1 [Visit 5], **and if these are not reported** would be the results reported on Day -14 [Visit 4]
 - If results on Day 1 [Visit 5] and on Day -14 [Visit 4] are missing the baseline will be considered as missing.

CCI

- For Adverse events, refer to definition of treatment-emergent outlined in Section 3.4.1, above

Change from baseline (CBL), relative change from baseline (RCBL) and percent change from baseline (PBL) will be calculated as follows:

- $CBL = \text{Observed Value} - \text{Baseline Value}$
- $RCBL = \text{Observed Value} / \text{Baseline Value}$
- $PBL = 100 \times (\text{Observed Value} - \text{Baseline Value}) / \text{Baseline Value}$

(NOTE: RCBL and PBL will not be considered for endpoints that can have a value of zero at baseline)

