5.2.1.2 Longitudinal Analysis

The over time effect of PF-05221304 on primary, secondary, and tertiary endpoints (see list in section 3) will be analyzed using the MMRM approach with randomized arm, time and randomized arm by-time interaction as fixed effects, subject as random effect using unstructured (UN) covariance structure. Baseline (in raw scale or log scale depending on the endpoint) will be included as covariate in the model.

Other covariance structures (eg Compound Symmetry (CS), Autoregressive(1) [AR(1)], Heterogeneous CS (CSH), and Heterogeneous AR(1) [ARH(1)]) will be considered if convergence in the previous model is not met.

The effect of PF-05221304 doses at all **post-randomization** visits will be estimated by the least-square (LS) means as well as LS mean differences against placebo respectively from the model described above.

For all analyses performed on log-transformed relative change from baseline (RCBL), the LS mean estimates and their corresponding confidence intervals (CIs) will be obtained for each randomized arm and week. Differences (and corresponding confidence intervals) between LS mean estimates will be obtained comparing randomized arms for each week. All LS means and LS mean differences (including CI's) will be back transformed to provide adjusted geometric LS means and ratios of adjusted geometric LS means. Then, percent change from baseline will be calculated as follows:

$$\text{Percent change} = 100 * (\text{RCBL} - 1)$$

where RCBL is either the adjusted geometric LS means estimate or the ratio of adjusted geometric means coming from the statistical model. The corresponding 80% CIs will be calculated as well.

For all analyses performed on raw scale, the LS means estimates and their corresponding confidence intervals (CIs) will be obtained for each randomized arm and week. Differences (and corresponding confidence intervals) between LS means will be obtained comparing randomized arms for each week.

Regardless if the data are analyzed in raw scale or after log-transformation, the inter- and intra-subject variability from the statistical model will be available and reported.

For % liver fat assessed by MRI-PDFP analyzed on log-scale, 80% confidence intervals will be presented for the LS geometric mean ratio.

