6.1.1 Primary Analysis on % Liver Fat assessed using MRI-PDF

Population: Entire Study Population

Endpoint: Relative change from baseline

Parameters: % Liver fat assessed with MRI-PDFP:

- Analysis time points: **all** applicable **post** Day 1/Visit 5 time points where **scheduled** assessment of specific continuous parameter is outlined in protocol
- Analysis population: FAS and PPAS (as sensitivity analysis).
- Analysis methodology: Log transformed relative change from baseline will be analyzed using MMRM model with log(baseline) as a covariate (specified in section 5.2.1.2).

Reporting results:

- Raw data and percent changes from baseline: Randomized subject, number of subject contributing to summary, sample size, mean, standard deviation, median, minimum, maximum, Q1 and Q3 at baseline and post-baseline visits will be presented for each randomized arm (see Appendix 2 for further detail).
- MMRM Outputs:
 - ✓ Adjusted geometric LS mean estimates with 80% confidence interval for each randomized arm along with the translation in percent change over time,
 - ✓ Ratio of adjusted geometric LS mean estimates for each active randomized arm against placebo and the corresponding 80% confidence interval along with the translation in percent difference over time.

Figures from MMRM outputs:

1. Line plot of percent change from baseline after back transformation of adjusted geometric LS means with 80% confidence interval over time (see Appendix 3.3),
2. Line plot of percent change from baseline placebo-adjusted after back transformation of adjusted geometric LS means ratios with 80% confidence interval over time (see Appendix 3.4),
3. Percent change from baseline after back transformation of adjusted geometric LS means with 80% confidence interval at Week 16 (see Appendix 3.5),
4. Percent change from baseline placebo-adjusted after back transformation of adjusted geometric LS means ratios with 80% confidence at Week 16 (see Appendix 3.6).

Note regarding the figures:

Instead of producing 4 independent figures, and in order to having a better understanding of the placebo effect, 1 figure containing side-by-side two panels presenting bullet 1 and 2 outputs (right panel for response over time and left panel for placebo adjusted response over time), and 1 figure with two panels presenting side-by-side bullet 3 and 4 outputs (right panel for response at Week 16 and left panel for placebo adjusted response at Week 16) should be produced.

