Weeks	Summary Statistics
Screen2, Baseline, and 4, 12, 16	N, arithmetic mean, median, %CV, standard deviation, minimum, maximum, Q1, Q3

Derived Parameters

Individual change from baseline, percent change from baseline and relative change from baseline for WLPDFF will be calculated and listed. Percent change from baseline will be summarized by randomized arm as described in Table A2.2-2.

Table A2.2-2: Summary Statistics for Percent Change From Baseline in % Liver Fat (WLPDFF) using MRI-PDFF

Weeks	Derived parameter	Summary Statistics
4, 12, 16	Percent Change from Baseline	N, arithmetic mean, median, standard deviation, minimum, maximum, Q1, Q3

Figures:

- Median response versus week will be presented against randomized arm. Q1 and Q3 values will be added.

- Median percent change from baseline versus week will be presented against randomized arm. A reference line cutting the Y-Axis at 0 will be overlaid. Q1 and Q3 values will be added.
- Box and whisker plots for individual percent change from baseline at week 16 versus total daily dose will be presented and overlaid with arithmetic means. Only box, whiskers, median, arithmetic mean, and outliers should be reported in this graphic. Total daily dose will be considered as categorical (see Appendix 3.1).

CCI

CCI

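### The liver-fat, ALT and other readable log-scale biomarker models adjust for one pre-dose value although a second is already collected; adding it is a modest, cheap gain in precision, not the repair of an error

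*SAP*

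**What the plan says.** SAP 5.2.1.2 sets the common longitudinal model and its one baseline term: "Baseline (in raw scale or log scale depending on the endpoint) will be included as covariate in the model". SAP 6.1.1 repeats this for liver fat, "Log transformed relative change from baseline will be analyzed using MMRM model with log(baseline) as a covariate", and SAP 6.2.1 and Appendix 1 do the same for ALT.

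SAP 3.5 makes that baseline a single value. For liver fat it is "defined as the value of total mean liver fat obtained between Visit 4 and Visit 5 (ie, labeled as baseline". For ALT and the others it is "Result closest prior to dosing on Day 1 [Visit 5] for the remaining pharmacodynamic endpoints". The Visit 4 result is only a fallback: if Visit 5 is not reported, the baseline "would be the results reported on Day -14 [Visit 4".

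More is collected before dosing than this uses:

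- **Liver fat.** Protocol Table 1 schedules MRI-PDFF at Screen 2 and again between Visits 4 and 5. SAP Table A2.2-1 summarises both ("Screen2, Baseline, and 4, 12, 16"), and SAP 7.2 uses MRI data up to Day 1 at the interim to estimate variability.
- **Laboratory values.** Protocol Table 2 schedules chemistry, including ALT, at Pre-Qualification, Screen 1, Visit 4 and Visit 5. The apolipoproteins, CK18 fragments, Pro-C3 and Pro-C6 are drawn at Visits 4 and 5.

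**The concern.** A single reading is a noisy measure of a subject's usual level. A second reading taken before randomisation can explain part of the outcome variance that the first leaves over, and it cannot bias the treatment comparison because it precedes allocation. If it is left out, the 80% intervals that compare four doses with placebo may be wider than the data require. The ALT comparison, planned on 30 completers per arm, would notice this most. Protocol 9.1 allows the trial to grow to 500 randomised subjects if the observed SDs exceed the assumed ones, so precision obtainable from data already in hand has some value.

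**Working it through.** **1. The plan's own power.** Protocol 9.1 for ALT: difference 35, SD 55, n = 30 per arm, one-sided 10%. The standard error is 55 × √(2/30) = 14.20, and 35/14.20 = 2.46. Subtracting 1.28 leaves 1.18, so power is 88.2% (87.8% with the t distribution). For liver fat at face value (difference 30, SD between 6.2 and √(7.8² + 6.2²) = 9.96), power is about 100% at 30 or 60 per arm. The claim of at least 80% therefore holds without any change.

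**2. Formula.** With log(baseline) as covariate, analysing log relative change leaves the same residual as analysing the log outcome, so what matters is how pre-dose values correlate with Week 16. Approximate the Week 16 contrast by an analysis of covariance. Let r1 be the correlation of the baseline with Week 16, r2 that of the earlier value with Week 16, and r3 that between the two pre-dose values.

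- One covariate: residual variance 1 − r1².
- Two covariates: 1 − (r1² + r2² − 2·r1·r2·r3)/(1 − r3²).
- If all three equal r, the ratio of two to one is (1 + 2r)/(1 + r)².

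**3. Liver fat.** Protocol 9.1 assumes that the "standard deviation for liver fat is 7.8% (between-subject) and 6.2% (within-subject"). At face value r = 60.84/(60.84 + 38.44) = 0.613. Rows 2 and 3 lower only r2 and keep r1 = r3 = 0.613.

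| Assumption | Variance ratio | Cut | 60 per arm is worth |
|---|---|---|---|
| All pairs 0.613 | 2.226/2.601 = 0.856 | 14% | 70 |
| r2 = 0.55 | 0.576/0.624 = 0.922 | 8% | 65 |
| r2 = 0.50 | 0.600/0.624 = 0.960 | 4% | 62 |
| First-order decay: r2 = r1 × r3 = 0.376 | 1.000 | 0 | 60 |

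In the best row the intervals narrow by 1 − √0.856 = 7.5%; with r2 = 0.50 they narrow by 2%.

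Screen 2 is also an entry threshold. A simulation with all pairs at 0.613, keeping only Screen 2 values of 8% or more and assuming mean liver fat of 15, 18 or 20%, gave ratios of 0.900, 0.890 and 0.883: a cut of 10–12%.

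**4. ALT, adding Visit 4.** The protocol gives no within-subject SD, so r is assumed. Treat 55 as the residual SD with one baseline.

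| r, all pairs | Variance ratio | SD | Power, n = 30 | 80% interval half-width |
|---|---|---|---|---|
| One baseline | 1 | 55 | 88.2% | 18.2 |
| 0.3 | 1.6/1.69 = 0.947 | 53.5 | 89.5% | 17.7 |
| 0.5 | 2.0/2.25 = 0.889 | 51.9 | 90.9% | 17.2 |
| 0.8 | 2.6/3.24 = 0.802 | 49.3 | 92.9% | 16.3 |

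The cut is 5–20%. If Visits 4 and 5 correlate at 0.7 with each other but each at 0.6 with Week 16, the ratio is [1 − 2(0.36)/1.7]/(1 − 0.36) = 0.576/0.64 = 0.90, a 10% cut. Under first-order decay it is again 0.

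**The case against.** The strongest objection is that Screen 2 is not a second baseline.

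- It is the scan that decides entry ("At Visit 2 (Screen 2), liver fat of" at least 8%), and one repeat is allowed.
- It precedes randomisation by a run-in of at least six weeks, during which Protocol 1.3.1 anticipates drift in liver fat, diet counselling starts, and lipid and blood-pressure drugs may be adjusted. It is therefore at least 6 + 16 = 22 weeks before Week 16.
- The single-reader aim in Protocol 7.1.3 and the segment matching in SAP Appendix 2.2.1 both start at baseline and leave Screen 2 out.

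All of this stands. It rules out averaging Screen 2 into the baseline and makes 14% an upper figure, not an expectation. It does not rule out a separate covariate, whose weight the data determine.

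It is also fair that 0.613 may not carry over. Protocol 9.1 does not say whether its SDs are liver-fat points or percent change, and the model works on the log scale. For ALT the documents supply no correlation at all.

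A reader might go further and infer three things the documents do not support:

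- That the trial is underpowered or its analysis biased. Step 1 shows the power claim holds, and one baseline covariate gives a valid comparison.
- That every pharmacodynamic endpoint is affected. Rows of Protocol Table 2 and part of SAP 3.5 are redacted, so this can be said only of the readable ones.
- That Screen 2 liver fat is merely tabulated. It also determines eligibility and falls within the interim variability data.

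**Conclusion.** The point holds as an optional efficiency gain. The models for liver fat, ALT and the other readable log-scale biomarkers use one pre-dose value where two exist, and the second can be used without touching the endpoint.

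The liver-fat gain is the less certain. The upper figure of about 14% needs equal correlation among all scans, the protocol SDs at face value and no effect of the entry threshold. The run-in makes the lower part of the range at least as credible. The Visit 4 covariate is the better supported of the two: it is taken two weeks before Visit 5, and Visit 4 ALT is not an entry criterion, unlike Pre-Qualification and Screen 1 ALT in subjects without biopsy-proven NASH. Its 5–20% range still rests wholly on assumed correlations.

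Any gain reaches only the pairwise contrasts from the repeated-measures models. The supportive liver-fat Emax analysis in SAP 6.1.2.1 is fitted without covariates and would not change.

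**What to change.** Amend the SAP before unblinding, leaving the endpoint and baseline definitions as they are.

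1. **SAP 5.2.1.2, 6.2.1 and 6.3.2:** for ALT and the other log-scale laboratory biomarkers, add log(Visit 4 value) as a second covariate.
2. **SAP 6.1.1:** add log(Screen 2 whole-liver PDFF) as a separate covariate. Where the scan was repeated, use the evaluable scan that determined eligibility. Compute it over the same liver segments as the subject's baseline where these are available.
3. **Missing or duplicated values:** where the earlier value is missing, or Visit 4 already serves as the baseline because Visit 5 is missing, substitute the pooled mean, blind to arm.
4. **SAP Appendix 1:** state that the rule of no imputation refers to outcomes, so that item 3 does not contradict it.
5. **SAP Appendix 1, model column:** list the added covariates.

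The cost is SAP wording and one degree of freedom per model, with no new samples or scans. If the sponsor is not persuaded about Screen 2, the Visit 4 covariate can be adopted on its own.

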5.2.1.3 Supportive Efficacy Analyses

The effect of PF-05221304 doses on % Liver Fat assessed with MRI-PDF **CCI** will be performed **post-database release** using the following dose-response model on the individual natural log transformed of relative change from baseline observed at Week 16.

Non-linear Dose-Response Model

The 3 parameter Emax model will be fit to the response at Week 16 on all doses. If the model converges, model estimated parameters will be presented along with their standard error (SE), 80% (Liver Fat **CCI**) confidence intervals as well as p-values (one-sided). The model projected placebo adjusted treatment effect for each PF-05221304 dose will also be presented along with their SE and confidence intervals. The Delta-Method will be employed to estimate standard errors and confidence intervals.

If the model fails to converge, the message “Algorithm fails to converge” will be displayed.

The 3-parameter Emax model is expressed as follows:

$$y_{ij} = E_0 + E_{\max} \frac{d_i}{d_i + ED_{50}} + \varepsilon_{ij}$$

, where y_{ij} denotes the response for subject j on dose i , d_i denotes dose i , and $\varepsilon_{ij} \sim \text{i.i.d } N(0, \sigma^2)$.

Alternative Dose-Response Model in case of no convergence

Selection of alternative dose-response model (eg linear, quadratic) may be explored after visual inspection of the response at Week 16. The rationale of the model selection and the subsequent analyses may be included in the CSR.

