### 1.3.3. Rationale for Doses Selected

In addition, to placebo, the PF-05221304 doses selected for this study (2, 10, 25 and 50 mg once daily) are based on the observed safety, tolerability, pharmacokinetic, and pharmacodynamic data from Study C1171001 in healthy adult subjects. In Study C1171001, PF-05221304 was found to be well tolerated with an acceptable safety profile with single doses up to 240 mg and repeated doses up to 200 mg/day administered and the MTD *not* identified. At the three highest doses ( $\geq 60$  mg/day), a gradual decrease in platelet count, was observed with repeated doses over the 14 day dosing period, though none of the values met the criteria for thrombocytopenia. In addition, a gradual increase in fasting and post-prandial triglycerides was observed with repeated doses  $\geq 40$  mg/day with effect plateauing over the 14-day dosing period.

Following repeated dosing in healthy adult subjects (Study C1171001), change from baseline in fructose-stimulated hepatic DNL was assessed via incorporation of deuterated water tracer into triglyceride-palmitate over a 10-hour period where fructose doses were given every 30-minutes to stimulate DNL. Inhibition in DNL, a marker of target engagement, was observed in a dose and concentration-dependent manner with  $\geq 90\%$  DNL inhibition at PF-05221304 total daily doses  $\geq 40$  mg/day. CCI

Given the projected degree of target engagement (ie, DNL inhibition) with the planned dosing frequency (ie, once-daily), PF-05221304 dosing frequency is proposed as once-daily (rather than Q12H evaluated on 5 of the 7 dose-levels in the Phase 1 Study C1171001 in healthy subjects). The selected dose range spans a range of expected DNL inhibition, allowing for assessment of the relationship between DNL and the primary endpoint (liver fat), key secondary endpoint (ALT), as well as safety and other parameters.

CCI

The overall dose selection of PF-05221304 was also influenced by the aim to identify not only a minimally-effective dose but also characterize the dose-response using the tablet strengths available (1, 5, 25, and 50 mg – with the 2 lower strengths looking identical but different than the 2 higher strength tablets) as efficiently as possible. As proposed, the dose-range planned will necessitate each subject to self-administer 3 tablets per day in order to maintain the double-blind design of this study.

CCI

CCI

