### 4.3. Randomization Criteria

- *At Pre-Qualification*, following completion of informed consent, subjects will be assigned a single 8-digit study-specific subject identification (SSID) number by the IRT (interactive response technology) system which will be retained throughout the duration of participation in the study;
- *At Visit 5 (Day 1)*, IRT will be used to assign each eligible subject a randomization number, with this number recorded on the electronic Case Report Form (e-CRF).
- A computer-generated randomization code using the method of random permuted blocks will be utilized to randomize subjects 1:1:1:1:1 (across placebo or 1 of 4 active doses of PF-05221304) at Visit 5 (Day 1) prior to the first dose of the double-blinded investigational product (PF-05221304 or matching placebo) provided subjects' satisfy **all** the following criteria:
  - Eligibility criteria outlined in [Section 4.1](#) and [Section 4.2](#);
  - A negative urine drug test for illicit drugs for sample collected at Visit 4 (Day -14) and results as reported by sponsor-identified central laboratory;
  - Fasting ( $\geq 8$  hours overnight, with water permitted) serum triglyceride result of  $\leq 400$  mg/dL (4.5 mmol/L), for sample collected at Visit 4 (Day -14), as reported by sponsor-identified central laboratory;
  - In females, *serum* pregnancy test at Visit 4 (Day -14) as reported by sponsor-identified central laboratory **and** *urine* pregnancy test *on-site* (in females of childbearing potential) at Visit 5 (Day 1) as reported on-site using supplies offered by sponsor-identified central laboratory, are negative for pregnancy – refer to [Section 7.3.1](#);
  - Noted to be  $\geq 90\%$  compliant (based on pill count) with the single-blind placebo administered from Visit 4 (Day -14) to *1 day before* Visit 5 (Day 1), inclusive, for a total duration of  $14 \pm 2$  days;
  - Total score of  $< 8$  on the AUDIT questionnaire, as assessed at Visit 5 (Day 1).
- Study will employ 2-tier stratification as outlined in [Figure 3](#).

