5 GENERAL METHODOLOGY AND CONVENTIONS

5.1 Hypotheses

Statistical inference will be made on the primary endpoint: percent change from baseline at Week 16 (Visit 11) in % liver fat assessed using MRI-PDFF. The null hypothesis is that there is no difference between PF-05221304 and placebo on the primary endpoint. The alternative hypothesis is that PF-05221304 is superior to placebo on the primary endpoint.

Mathematically, the null and alternative hypotheses are expressed as follows.

$$H_0 : \mu_i - \mu_0 = 0$$

vs.

$$H_a : \mu_i - \mu_0 < 0 ,$$

where μ_i is the mean percent change from baseline for PF-05221304 doses of 2 mg QD, 10 mg QD, 25 mg QD and 50 mg QD, and μ_0 is the mean percent change from baseline for placebo.

Statistical inferences for the primary endpoint will be done at a one-sided significance level of 10%. A dose is considered efficacious if the lower 90% lower confidence limit of $\mu_1 - \mu_0$ exceeds 0.

No Adjustment will be made for multiple comparisons.

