6.1.2 Supportive Analyses on % Liver Fat Assessed using MRI-PDFF

6.1.2.1 Dose-Response Model

For % Liver Fat assessed by MRI-PDFF at Week 16, the analysis will be performed on the FAS without covariates in subject with nonalcoholic fatty liver disease (entire study population). The primary endpoint is the log transformed relative change from baseline in liver fat at Week 16 using the dose response model as described in section 5.2.1.3.

Endpoint: Relative change from baseline

Parameter: % Liver fat assessed by MRI-PDFF

- Analysis time points Week 16
- Analysis population: FAS in subject with nonalcoholic fatty liver disease (entire study population)
- Analysis methodology: Natural log-transformed relative change from baseline in % liver fat will be analyzed using the Dose-Response model (specified in section 5.2.1.3).
- Supporting objective: Primary Objective

Reporting results for model:

- The three parameters of the Emax model (E0, ED50, and Emax) along with their respective 80% confidence interval if non-linear model. .

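### The SAP does not state the scale of the 80% interval for ED50; if it is symmetric in mg, its upper limit is too low more often than the nominal 10%

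*SAP*

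**What the plan says.** SAP 5.2.1.3 states: "The 3 parameter Emax model will be fit to the response at Week 16 on all doses". The displayed equation has ED50 itself as a parameter, on the same scale as dose, and the response is the log relative change from baseline in liver fat. If the fit converges, the parameters are presented with standard errors, 80% intervals and one-sided p-values. The next sentence adds the model-projected placebo-adjusted effect for each dose, with its own SE and interval. Then comes the only statement of method: "The Delta-Method will be employed to estimate standard errors and confidence intervals".

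SAP 6.1.2.1 lists as the reported result "The three parameters of the Emax model (E0, ED50, and Emax) along with their respective 80% confidence interval if non-linear model". It ties this analysis to the primary objective, which is dose-response.

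Neither section names the scale of the ED50 interval, a positivity bound, a log(ED50) form, profile likelihood or a bootstrap.

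**The concern.** ED50 must be positive, and with four active doses its estimate is right-skewed. Its delta-method SE grows faster than the estimate does: a trial that under-estimates ED50 also under-estimates its SE, and a trial that over-estimates ED50 gets a very wide interval. A symmetric interval in mg therefore places nearly all its misses on one side, with the upper limit too low. Its lower limit can be below 0 mg. Neither effect needs the Emax model to be wrong.

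ED50 is the parameter that locates the curve on the dose axis, and Protocol 1.3.3 says the doses were chosen partly to characterise dose-response. An upper limit that is too low understates how high the half-maximal dose could be.

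**Working it through.** **Plan's own figure.** The documents give no error rate for this interval beyond the 80% level, which implies 10% per tail if equal-tailed. The power statement in Protocol 9.1 does reproduce (ALT: difference 35, SD 55, 30 per arm, one-sided 10% gives 88.2%, consistent with at least 80%), but it says nothing about ED50.

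**Inputs from the documents.** Placebo plus "2, 10, 25 and 50 mg once daily" (Protocol 1.3.3). The plan is to "randomize subjects 1:1:1:1:1" (Protocol 4.3), with "at least 300 subjects (60 subjects per arm) complete the study" (Protocol 9.1). No covariates in the Emax fit (SAP 6.1.2.1).

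**Assumptions.** The readable text gives no true ED50, no Emax and no SD of the log relative change. Ranges used: ED50 2-20 mg; a reduction of 30-65%, taken either as the maximal effect or as the effect at 50 mg; SD 0.30-0.73. One anchor for the SD is sqrt(2) x 6.2 / mean baseline liver fat, using the within-subject SD in Protocol 9.1: 0.44, 0.55 and 0.73 at assumed baselines of 20, 16 and 12%.

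**Delta-method SE.** Let g = d/(d+ED50) and h = d/(d+ED50)^2 at the five doses, and let R be the residual sum of squares from regressing h on g with an intercept. Then SE(ED50) = SD / (sqrt(60) x |Emax| x sqrt(R)). At ED50 10 mg, R = 0.0002102. With SD 0.4 and Emax = ln 0.5 = -0.693, SE = 0.4 / (7.746 x 0.693 x 0.01450) = 5.14 mg.

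**Why the tails are unequal.** Keep SD 0.4 and hold Emax at -0.6. The SE is 2.51 mg at ED50 5, 5.94 mg at 10 and 15.53 mg at 20. The 80% multiplier is t(0.90; 297 df) = 1.284. Suppose the truth is 10 mg.

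- Estimate 5 mg: upper limit 5 + 1.284 x 2.51 = 8.2 mg, which misses the truth.
- Estimate 20 mg: lower limit 20 - 1.284 x 15.53 = 0.1 mg, which covers it easily.

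The lower limit is negative whenever SE/estimate exceeds 1/1.284 = 0.78.

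**Simulation with the Emax model true.** 60 per arm, SD 0.4, 6,000 trials per row. Entries are % of trials with an interior ED50 estimate (98-100% of trials here); nominal is 10% per tail.

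| Emax | ED50 (mg) | mg scale: upper too low | mg scale: lower too high | mg scale: coverage | mg scale: lower < 0 | log(ED50): upper too low / lower too high | Profile: upper too low / lower too high |
|---|---|---|---|---|---|---|---|
| -0.6 | 5 | 15.6 | 1.0 | 83.4 | 0.4 | 10.4 / 9.8 | 9.3 / 10.6 |
| -0.6 | 10 | 16.8 | 0.0 | 83.2 | 7.6 | 10.7 / 8.6 | 9.8 / 10.5 |
| -0.6 | 20 | 19.1 | 0.0 | 80.9 | 53.0 | 11.6 / 0.2 | 9.7 / 9.1 |
| -0.8 | 5 | 14.1 | 3.7 | 82.2 | 0.0 | 10.1 / 10.0 | 9.2 / 10.5 |
| -0.8 | 10 | 15.6 | 0.7 | 83.8 | 0.1 | 10.3 / 9.4 | 9.7 / 10.6 |
| -0.8 | 20 | 17.0 | 0.0 | 83.0 | 12.3 | 11.0 / 4.1 | 9.5 / 10.4 |

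Repeat runs on this grid agree to within about one percentage point, hence about 15-20%, with the most favourable corner just under 15%.

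**Wider grid** (5,000-10,000 trials per scenario):

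- Precise case (SD 0.3, maximal reduction 65%, ED50 5 mg): upper limit too low in 12.3%.
- SD 0.55, 50% reduction at 50 mg, ED50 2-20 mg: 15.1-18.0%; lower limit negative in 1.6-24.8%.
- SD 0.55, 30% reduction at 50 mg, ED50 2-20 mg: 16.4-25.3%; negative in 89.5-97.5%.
- SD 0.73, 30% reduction at 50 mg, ED50 20 mg: 29.0%; negative in 99.7%; coverage 71.0%.
- Whole grid: upper limit too low in about 11-30%, above 10% in every scenario; lower limit too high in 0-8%; coverage mostly 80-85%, falling to 70-79% in the weak scenarios.

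A subject-level nonlinear least-squares check at SD 0.4, Emax ln 0.5 and ED50 10 mg gave 16.5% above and 0.1% below.

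**The case against.** The strongest reply is that the SAP never says the ED50 interval is symmetric in mg. It gives no interval formula, and the delta-method sentence follows directly on the per-dose projected effects, which are functions of the parameters and the usual place for that method. A reader might infer that the SAP prescribes a faulty interval. The text does not go that far: the mg-scale interval is the natural default for a model written in ED50 with an SE reported for it, but it is a reading. That stands, and it is why the point is about an unspecified scale. It does not remove the point, because two programmers could follow this text and report different limits.

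Second, the SAP promises an 80% interval, and two-sided coverage is close to that in most scenarios. This also stands. The fault is where the limits sit.

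Third, any single percentage depends on unstated inputs. A reader might take 15-20% as a property of this trial; it belongs to one set of assumptions within a range of about 11-30%. Negative lower limits are rare when ED50 is low and the effect strong, and a negative limit is easily read as zero.

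Fourth, a reader might infer that the ED50 limits decide which doses go forward. No section says so. SAP Appendix 1 labels the Emax fit supportive, Protocol 9.2.1 calls the modelling exploratory, and SAP 5.1 judges each dose by its difference from placebo.

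**Conclusion.** The point holds as a gap in specification with a predictable consequence. If the ED50 interval is computed as estimate plus or minus t times SE in mg, the upper limit is too low in more than the nominal 10% of trials in every scenario examined, with the sizes given above. The direction is stable; the size rests on assumed values of ED50, Emax and the log-scale SD.

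All rates are among fits with an interior ED50 estimate (80-100% of trials over the wide grid), since non-converged fits get no interval under the SAP. Importance is low: the effect is confined to a supportive analysis of the primary dose-response objective.

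**What to change.** In SAP 5.2.1.3 and 6.1.2.1, state that the 80% interval for ED50 is by profile likelihood: all ED50 values for which the residual sum of squares, after re-fitting E0 and Emax, exceeds its minimum by no more than the residual variance times the 80th percentile of F(1, N-3). This is the preferred option; its upper limit is too low in about 9-11% of trials in most scenarios (5-12% over the whole grid).

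The alternative is to estimate log(ED50) and back-transform its limits. These are always positive, but some imbalance remains: the lower-tail miss was 0.2% at ED50 20 mg with Emax -0.6 and SD 0.4, and the upper-tail miss ranged from 0 to about 15% over the whole grid.

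Keep the delta method for E0, Emax and the per-dose effects, and say that this is what the existing sentence covers. SAP Appendix 1 sends the ALT dose-response model to the same section, so the wording would apply there too; its size was not calculated.

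The cost is one SAP sentence and a few lines of code. The downside is an upper limit that may be larger, or open-ended when the data do not bound ED50, and it should be reported as such.
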